5.2 Secondary Objectives and Endpoints

To evaluate safety and tolerability of hepatic ultrasound insonification in subjects with T2DM, assessed by:

- Incidence and severity of adverse device effects (ADEs) [including, liver injury]
- Incidence and severity of clinically significant laboratory abnormalities
- Change from baseline in vital signs (blood pressure, temperature, respiratory rate, and heart rate)
- Incidence and severity of clinical findings on physical examination
- Change from baseline in 12-lead electrocardiogram (ECG) parameters; the primary ECG endpoint will be QTcF

To evaluate the effect of hepatic ultrasound insonification on changes from baseline in whole-body insulin sensitivity during a two-step hyperinsulinemic, euglycemic clamp (H-E Clamp), assessed by:

- Insulin Sensitivity Index (SI)
- Glucose disposal rate during steady state (M)
- Glucose metabolic clearance rate during steady state (MCR)

To evaluate the effect of hepatic ultrasound insonification on change from baseline in glucose tolerance and insulin secretion, assessed by an oral glucose tolerance test (OGTT)

- Area under the curve (AUC), total and incremental time, e.g., $AUC_{0-180\text{min}}$

To evaluate the effect of hepatic ultrasound insonification on glucose metabolism parameters, assessed by:

- Change from baseline in blood glucose (BG) profiles assessed with continuous glucose monitoring system (CGMS)
 - Time spent in defined glucose ranges

- Average daily glucose
 - BG variability parameters (e.g., coefficient of variation as percentage of mean level [% CV], etc.)
 - Low blood glucose index (LBGI)
 - High blood glucose index (HBGI)
- Change from baseline in Homeostasis Model Assessment of Insulin Resistance (HOMA-IR)
 - Change from baseline in Homeostatic Model Assessment of Insulin Secretion (HOMA-B)
 - Change from baseline in fasting plasma glucose (FPG)

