6.3 Rationale for Study Design and Endpoints

The aim of this exploratory, pilot study is to determine the effect of hepatic ultrasound insonification on insulin sensitivity, glycemic, metabolic and lipid parameters, as well as on various biomarkers in subjects with T2DM.

Subjects with T2DM will participate in the study, as these subjects are an important target population. These subjects are characterized by relative rather than absolute insulin deficiency in association with variable degrees of insulin resistance.

Subjects on metformin therapy will continue the stable drug dose throughout the entire study.

Subjects will be supplied with a CGMS to ensure that blood glucose levels are monitored closely. CGM as assessment has been chosen to assess the ultrasound insonification effects with a standardized method for efficacy. As assessment of insulin secretion and resistance, an OGTT and H-E clamp will be performed.

Whole-body insulin sensitivity will be assessed with the 2-step H-E clamp procedure. The use of two-stepped IV insulin infusions is used in combination with IV stable isotope labeled glucose infusion to allow the differentiation between hepatic (EGP) and peripheral insulin sensitivity.

Due to the variability in fasting blood glucose concentrations in subjects with diabetes mellitus, which might affect the metabolic response, an overnight baseline period will be

used to establish the target plasma glucose concentration of 100 mg/dL ($\pm 10\%$) prior to fasting EGP measurements.

Endogenous glucose production will be measured in the fasting state prior to the start of the clamp and suppression of EGP during step 1 of the 2-step H-E clamp. It will be assessed using a stable isotope labeled glucose ($[6,6-^2\text{H}_2]\text{glucose}$) tracer method.

Insulin will be infused at a low dose, followed by a high dose. During the low-dose IV insulin infusion, EGP will be partially suppressed, while during the high dose IV insulin infusion, EGP will be near completely suppressed.

Metabolic changes in response to glucose ingestion will be assessed via an OGTT. It will be performed to assess the postprandial carbohydrate metabolism to see changes in insulin and glucose response.

The other glucometabolic endpoints of this study are chosen to investigate additional ultrasound insonification effects.

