9.1.19 Oral Glucose Tolerance Test (OGTT)

An oral glucose tolerance test (OGTT) will be administered at the time points specified in the [Schedule of Events \(SOE\)](#).

Subjects will be fasted \geq 10 hours prior to the OGTT. At approximately 08:00 h-09:00 h the OGTT will begin. Subjects will be asked to drink 75 g of glucose in a 10-fluid ounce beverage over 5 minutes. The glucose ingestion will be followed by approximately 100 mL of water. The subject will rest for the duration of test and will abstain from eating. Only small amounts of water may be consumed for the duration of the test. Sampling for fasting glucose, C-peptide, insulin sampling will be performed before the OGTT and 15, 30, 60, 90, 120, 150 and 180 min after the start of the glucose administration.

The time of all blood draws and the time when the subjects start to drink the glucose solution will be recorded.

OGTT sampling schedule: Time points are relative to start of OGTT procedure. All samples will be taken within a window of \pm 3-minutes.

All OGTT procedures during the in-house periods on Day 1 and Day 16 will follow the same schedule.

The OGTT procedure for each subject (inter-individual) will start one hour (nominal time) after the start of their hepatic ultrasound insonification. A window of \pm 15 minutes will be allowed.

Insonification and OGTT on Days 1 and 16 should start at the same time (actual time) for each subject (intra-individual).

Table 9-2 Sampling Schedule for OGTT

Nominal time (min) relative to Start of OGTT	-15	0	15	30	60	90	120	150	180
Standard Test Solution (75 g dextrose)		X							
Plasma Glucose	X		X	X	X	X	X	X	X
Insulin and C-peptide	X		X	X	X	X	X	X	X

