9.1.22 Two-step Hyperinsulinemic, Euglycemic Clamp

On the evening prior to the clamp procedure, subjects will receive a standardized dinner, which will be followed by an approximately 10-hour overnight fast.

Subjects will receive an overnight insulin IV infusion to achieve plasma glucose levels of approximately 100 ± 10 mg/dL during the last two hours of the overnight IV infusion prior to the fasting EGP assessment period.

Subjects will be connected to the Biostator prior to the start of the clamp procedure.

During step 1 and step 2 of the clamp procedure, insulin will be infused at two infusion rates each lasting approximately 180 minutes and D20W will be enriched with stable isotope labeled glucose to achieve a stable isotope glucose enrichment comparable to that of plasma in the fasting state (e.g., 2.5 to 3% for plasma [6,6-²H₂]glucose). Insulin will be infused IV by means of a precision pump for 180 min at the following rate:

Step 1: For the Step 1 insulin infusion of the clamp procedures at Day 2, an amount of 10 mU/m²/min will be added to the average insulin infusion rate which was provided per algorithm over the last 2 hours of the overnight infusion. This will be calculated for each individual subject.

For the Step 1 insulin infusion of the clamp procedures at Day 17, the insulin infusion rate should be identical to the rate used at Day 2. It is important that each subject receives the same insulin infusion rate on Day 17 that he/she received on Day 2.

Step 2: After 180 minutes (end of Step 1), the insulin infusion will be increased to 120 mU/m²/min for a further 180 minutes (Step 2) of the clamp for all subjects at Day 2 and Day 17. This will provide supraphysiological insulin concentrations that will near-maximally stimulate glucose disposal. EGP is expected to be near maximally suppressed.

The glucose infusion rate (GIR; 20% v/v) required to maintain arterialized venous blood glucose (glucose oxidase method) at the target level of 100 ± 10 mg/dL will be recorded throughout the clamp. The steady-state period for insulin sensitivity measurements is

defined as the time from 150 to 180 minutes following the initiation of the continuous insulin infusion during each step, and the GIR recorded during the last 30 minutes (steady-state) of each insulin infusion step is used for the determination of insulin sensitivity. Blood samples for the determination of plasma glucose will be drawn at scheduled time points before and during the clamp.

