2.2. Secondary Objectives and Endpoints

To evaluate safety and tolerability of hepatic ultrasound insonification in subjects with T2DM, assessed by:

- Incidence and severity of adverse device effects (ADEs) [including, liver injury]
- Incidence and severity of clinically significant laboratory abnormalities
- Change from baseline in vital signs (blood pressure, temperature, respiratory rate, and heart rate)
- Incidence and severity of clinical findings on physical examination
- Change from baseline in 12-lead electrocardiogram (ECG) parameters; the primary ECG endpoint will be QTcF

To evaluate the effect of hepatic ultrasound insonification on changes from baseline in whole-body insulin sensitivity during a two-step hyperinsulinemic, euglycemic clamp (HE Clamp), assessed by:

- Insulin Sensitivity Index (SI)

- Glucose disposal rate during steady state (M)
- Glucose metabolic clearance rate during steady state (MCR)

To evaluate the effect of hepatic ultrasound insonification on change from baseline in glucose tolerance and insulin secretion, assessed by an oral glucose tolerance test (OGTT)

- Area under the curve (AUC), total and incremental time, e.g., $AUC_{0-180\text{min}}$

To evaluate the effect of hepatic ultrasound insonification on glucose metabolism parameters, assessed by:

- Change from baseline in blood glucose (BG) profiles assessed with continuous glucose monitoring system (CGMS)
 - Time spent in defined glucose ranges
 - Average daily glucose
 - BG variability parameters (e.g., coefficient of variation as percentage of mean level [% CV], etc.)
 - Low blood glucose index (LBGI)
 - High blood glucose index (HBGI)
- Change from baseline in Homeostasis Model Assessment of Insulin Resistance (HOMA-IR)
- Change from baseline in Homeostatic Model Assessment of Insulin Secretion (HOMA-B)
- Change from baseline in fasting plasma glucose (FPG)

2.3.Exploratory/Other Objectives and Endpoints

To evaluate the effect of hepatic ultrasound insonification on glucose/metabolism parameters, assessed by:

- Change from baseline in exploratory biomarkers (blood samples will be stored for potential later analysis), e.g., but not limited to:
 - Glucagon
 - Glucagon-like peptide 1 (GLP-1), total
 - Leptin
 - Ghrelin
- Change from baseline in long-term glucose parameters
 - Hemoglobin A1c (HbA1c)
 - Fructosamine
- Change from baseline in lipid metabolism parameters
 - Free fatty acids (FFAs)
 - Triglycerides (TG)
 - Total cholesterol

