5. GENERAL DATA HANDLING CONSIDERATIONS

All analyses will be conducted using SAS 9.4 or higher.

All data in the database will be presented in by-subject data listings.

Unless otherwise stated, all listings will be sorted by site ID, subject number, and assessment date (and time, if available).

Unless stated otherwise, continuous data will be summarized by number of subjects (n), mean, median, standard deviation (SD), first quartile (Q1), third quartile (Q3), minimum value, and maximum value.

Unless stated otherwise, categorical data will be summarized n and percentage based on the number of non-missing values. Where applicable, the number of missing values will be presented as a separate category with no percentage. Counts of zero will be presented without percentages.

The following precision will be used when presenting data:

- Minimum and Maximum: same number of decimal places as reported in the original data
- Mean, Median, Q1, and Q3: one additional decimal place to that reported for Minimum and Maximum
- SD: two additional decimal places than the Minimum and Maximum
- Percentages: reported to one decimal place
- P-values will be reported to four decimal places. If the value is below 0.0001 it will be noted as < 0.0001; if the value above 0.9999 it will be noted as > 0.9999.

Study data will not be reviewed for purpose of comparison between cohorts/groups. However, if statistical testing is performed, statistical inference will be based on a 5% significance level (i.e. 95% confidence intervals will be produced) and details will be provided in the CSR.

All data up to the time of study completion/withdrawal from the study will be included in the analysis, regardless of duration of treatment.

Numbering for data displays will be based on ICH E3 when applicable.

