In addition to the continuous summary, the overall interpretation of ECG results will be summarized as within normal limits, abnormal without clinical significance, and abnormal with clinical significance by visit and time point.

All ECG data will be listed.

Whole-body insulin sensitivity

The effect of hepatic ultrasound insonification on changes from baseline in whole-body insulin sensitivity during a two-step HE Clamp will be assessed by:

- Insulin Sensitivity Index (SI)
- Glucose disposal rate during steady state (M)
- Glucose metabolic clearance rate during steady state (MCR)

The formulas for SI, M, and MCR are described in section 6.8. Each parameter will be summarized using descriptive statistics in the Ultrasound Insonification Effect Population.

Glucose tolerance and insulin secretion

To evaluate the effect of hepatic ultrasound insonification on change from baseline in glucose tolerance and insulin secretion, assessed by an oral glucose tolerance test (OGTT), area under the curve (AUC) total and incremental time (e.g., $AUC_{0-180\text{min}}$) will be calculated.

AUC is calculated according to the linear trapezoidal rule:

$$\frac{AUC(t_i)}{t_{i+1}} = \frac{C_i + C_{i+1}}{2} \times (t_{i+1} - t_i)$$

where C is glucose concentration (mg/dL) with measurements at times $t_1..t_n$ such that

$$AUC_{\text{total}} = \sum_{i=1}^{n-1} AUC(t_i)$$

$AUC_{0-180\text{min}}$ is similarly derived but uses data only through 180 minutes.

AUC results will be summarized using descriptive statistics in the Ultrasound Insonification Effect Population.

Glucose metabolism parameters

The effect of hepatic ultrasound insonification on glucose metabolism parameters will be evaluated by the following endpoints in the Ultrasound Insonification Effect Population:

- Blood glucose (BG) profiles assessed with continuous glucose monitoring system (CGMS)
 - Time spent in defined glucose ranges
 - Average daily glucose
 - BG variability parameters (e.g., coefficient of variation as percentage of mean level [% CV], etc.)
 - Low blood glucose index (LBGI)
 - High blood glucose index (HBGI)
- Homeostasis Model Assessment of Insulin Resistance (HOMA2-IR)
- Homeostatic Model Assessment of Insulin Secretion (HOMA2-B)
- Fasting plasma glucose (FPG)

The baseline period for CGMS parameters will be calculated using data starting from 14:00h on Day -1 to 22:00h on Day 1, omitting data collected between a subjects OGTT glucose consumption start time + 180 minutes.

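### SAP 6.9 defines the OGTT AUC for glucose only, so the insulin-secretion part of the secondary OGTT objective has no prespecified summary

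*SAP*

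**What the plan says.** Protocol 5.2 sets a secondary objective of "change from baseline in glucose tolerance and insulin secretion, assessed by an oral glucose tolerance test (OGTT"), and SAP 2.2 repeats it. The endpoint listed beneath it in both documents is an AUC, total and incremental, with no analyte named. Protocol 6.3 gives the reason for the test: it is done "to see changes in insulin and glucose response".

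Protocol 9.1.19 sets the blood draws: "Sampling for fasting glucose, C-peptide, insulin sampling will be performed before the OGTT and 15, 30, 60, 90, 120, 150 and 180 min" after the drink is started. Table 9-2 places the pre-drink draw at -15 min. Its 0-min column marks only the glucose drink. Days 1 and 16 follow the same schedule.

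SAP 6.9, under a subheading that names both glucose tolerance and insulin secretion, gives one linear trapezoidal formula, "where C is glucose concentration (mg/dL) with measurements at times" t1 to tn. It defines AUC_total as the sum over intervals and AUC0–180min as the same quantity restricted to data through 180 minutes. Only these AUC results are then summarized, in the Ultrasound Insonification Effect Population.

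**The concern.** The objective has two parts and the formula serves one. Because the SAP states both the analyte and its unit, C cannot be read as a generic concentration. A programmer who follows SAP 6.9 would produce glucose AUCs and nothing for insulin secretion.

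What is at stake is the response to the glucose load. In an open-label, single-cohort study, an insulin measure chosen once the data are in hand is open to the criticism that it was picked for its result. Calling the analysis descriptive does not remove the need to say beforehand which result will be described.

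**Working it through.** No sample-size, power or alpha figure bears on this point. SAP 3.3 says no formal calculation was made, so there is no plan figure to reproduce. The check is a comparison of sections and a count.

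**1. Objective against analysis**

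| Element | Glucose | Insulin / C-peptide |
|---|---|---|
| Secondary OGTT objective (Protocol 5.2, SAP 2.2) | yes, as glucose tolerance | yes, as insulin secretion |
| OGTT rationale (Protocol 6.3) | yes | yes, as insulin response |
| OGTT samples (Protocol 9.1.19, Table 9-2) | 8 times, Days 1 and 16 | 8 times, Days 1 and 16 |
| AUC formula and summary (SAP 6.9) | yes | none |

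**2. Values without an OGTT summary**

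- Times per test: 1 pre-drink + 7 post-load (15, 30, 60, 90, 120, 150, 180 min) = 8.
- Per subject: 2 tests × 8 times × 2 analytes = 32.
- For 15 completers: 32 × 15 = 480, that is 240 insulin and 240 C-peptide.

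**3. Does another part of the SAP supply the result?**

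- *HOMA2-B (SAP 6.9).* It is listed as its own endpoint and computed from fasting plasma glucose and insulin taken from the safety laboratory. It describes fasting secretion, not the response to the drink.
- *Clamp.* Under Protocol 9.1.22, "insulin will be infused at two infusion rates each lasting approximately 180 minutes", so measured insulin includes the infused insulin. Table 9-3 draws no C-peptide, so the clamp gives no result for post-load secretion.
- *Laboratory summaries (SAP 6.9).* These cover safety laboratory evaluations by visit. Protocol Table 9-1 lists only fasting insulin and fasting C-peptide.
- *Listings (SAP 5).* "All data in the database will be presented in by-subject data listings", so the values can be seen subject by subject, but they are not summarized.
- *C-peptide.* The SAP text does not mention it. Insulin enters SAP calculations only for the clamp and HOMA2.

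**4. Time rule, a side matter that affects any analyte**

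Table 9-2 has no 0-min blood sample. Protocol 9.1.19 also says "All samples will be taken within a window of" ±3 minutes, so the last draw may fall as late as 183 min. Two readings based on literal sampling times would change the interval covered:

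- Starting the sum at the -15 min sample: 180 − (−15) = 195 min; 195/180 − 1 = 8.3% more minutes.
- Dropping a last draw taken after 180 min: the AUC ends at 150 min; 30/180 = 16.7% of the minutes lost.

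Both percentages are shares of time, not of AUC, and both arise only if the rule is applied in that literal way.

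**The case against.** The strongest reply is that little turns on this. The study is an exploratory pilot of about 15 subjects, the analysis is descriptive, the values are collected and listed, and fasting insulin secretion is still summarized through HOMA2-B. A summary could be added at any time. All of that is true, and it limits the weight of the point. It does not answer it: the objective says secretion is assessed by OGTT, HOMA2-B is not an OGTT measure, and a late addition would not be prespecified.

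A second reply is that the objective does not require AUCs of both insulin and C-peptide. This stands. The documents call for an OGTT result on insulin secretion without naming the analyte or the index. Using both is a reasonable choice because both are drawn; the documents do not dictate it.

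A reader might also infer three stronger things that the documents do not support:

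- *That SAP 7 conceals a dropped analysis.* SAP 7 speaks of analyses specified in the protocol. Protocol 12.1.3 describes clamp, EGP and Rd analyses and no OGTT analysis, and the AUC endpoint names no analyte. The SAP falls short of its objective, but it is not shown to have made an undeclared change.
- *That the planned glucose AUC is wrong by 8.3% or 16.7%.* Table 9-2 labels its times as nominal, and SAP 5.6 bases summaries on nominal visits. That section is about visits rather than minutes, so a clarifying line is useful, but the losses depend on an unlikely reading.
- *That the schedule of events settles when HOMA-B is measured.* It has a HOMA-IR row and no HOMA-B row, so nothing here rests on HOMA-B timing.

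**Conclusion.** The point holds for the analyte gap. Followed as written, SAP 6.9 reports the glucose-tolerance part of a stated secondary objective and gives no summarized OGTT result for insulin secretion, although 32 insulin and C-peptide values per subject (480 for 15 completers) are scheduled for that test.

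The consequence is bounded. M/I, EGP and Rd are untouched, insulin sensitivity is still measured by the clamp, and no data are lost. What is missing is a prespecified result. The correction is worth making because it is nearly free, not because the trial's main conclusions are at risk.

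This assumes that the SAP is applied as worded, that Table 9-2 is read as eight blood draws per test, and that 15 subjects complete both OGTTs.

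**What to change.** In SAP 6.9:

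1. Let C be glucose (mg/dL), insulin and C-peptide, the last two in the units the laboratory reports.
2. Compute AUC0–180min for each by the same trapezoidal rule.
3. Summarize Day 1, Day 16 and the Day 16 minus Day 1 change for each analyte descriptively in the Ultrasound Insonification Effect Population.

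As a clarification in the same edit:

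4. State that the nominal times of Table 9-2 are used, with the -15 min sample as the time-0 value on both days and the nominal 180-min sample always included, even if drawn up to 3 minutes late.
5. State what incremental AUC means, and keep both the total and the incremental output, since the protocol and SAP name both.

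The cost is SAP wording, the same AUC program run on two more analytes, and a few more descriptive tables. No new samples or visits are needed.

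### SAP 6.9 computes one OGTT AUC under two labels, and no AUC that separates a shift in glucose level from the response to the drink

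*SAP*

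**What the plan says.** Protocol 5.2 lists the secondary OGTT endpoint as "Area under the curve (AUC), total and incremental time, e.g"., with AUC0–180 min as the only example. SAP 6.9 (Glucose tolerance and insulin secretion) repeats it as "area under the curve (AUC) total and incremental time (e.g"., with the same example.

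SAP 6.9 then gives one computing rule: "AUC is calculated according to the linear trapezoidal rule". The symbols are defined by "where C is glucose concentration (mg/dL) with measurements at times" t1 to tn, and AUC_total is the sum of the trapezoids over all those times. AUC0–180 "is similarly derived but uses data only through 180 minutes". The section has no subtraction of a fasting value, no lower time limit and no interval other than the full test.

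Protocol 9.1.19 sets the sampling: "before the OGTT and 15, 30, 60, 90, 120, 150 and 180 min after the start of the glucose administration". Table 9-2 puts the pre-drink sample at −15 min and only the drink at 0. Each sample has a window of ±3 min, and actual draw times are recorded. The test is done on Day 1 and Day 16 on the same schedule.

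**The concern.** An endpoint described with two terms, total and incremental, should lead to at least two defined quantities. The SAP appears to give two, but the limit that distinguishes them removes no scheduled sample. The 0–180 label also does not match the sampling times to which the formula is applied.

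The stake is interpretation. Protocol 6.3 includes the OGTT to study the response to ingested glucose. The target is the liver and endogenous glucose production is a primary endpoint, so a change in basal glucose is a plausible result. On Day 16 the OGTT starts about one hour after insonification starts, so even its fasting sample is post-insonification. A raw AUC mixes the basal level with the response to the drink. If the whole curve moves down in parallel, the only AUC reported falls and could be taken as better glucose tolerance although the excursion is unchanged. Protocol 4.2 counts glucose tolerance among the markers by which a biological effect is to be judged.

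**Working it through.** The documents give no AUC value or variance, so there is no figure of the plan to reproduce. The check applies the SAP rule to the Table 9-2 times.

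**Inputs from the documents.** Glucose times are −15, 15, 30, 60, 90, 120, 150 and 180 min. The rule is the linear trapezoid, summed over all times.

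**Assumptions, not in the documents.** Fasting glucose F is 120 to 210 mg/dL. The rise above fasting at the seven post-drink times is 30, 70, 120, 140, 130, 100 and 70 mg/dL.

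**Step 1: weight of each sample (min).** These do not depend on the assumed curve.
- First sample at −15: 15, 22.5, 22.5, 30, 30, 30, 30, 15. Sum 195.
- First sample placed at 0: 7.5, 15, 22.5, 30, 30, 30, 30, 15. Sum 180.

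**Step 2: AUC_total against AUC0–180.** At F = 150 the values are 150, 180, 220, 270, 290, 280, 250 and 220.
- SAP sum: 15×150 + 22.5×180 + 22.5×220 + 30×(270+290+280+250) + 15×220 = 2,250 + 4,050 + 4,950 + 32,700 + 3,300 = 47,250 mg·min/dL.
- Restricted to times up to 180: the same eight samples, so 47,250 again.

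**Step 3: effect of the −15 start on the level.** With the fasting sample at 0, the sum is 1,125 + 2,700 + 4,950 + 32,700 + 3,300 = 44,775. The excess is 7.5 × (fasting value + 15-min value) = 7.5 × (150 + 180) = 2,475.

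**Step 4: parallel fall of every sample by d.** The SAP sum changes by −195 × d, or −180 × d with the fasting sample at 0. Net incremental AUC, defined as AUC0–180 − 180 × F, changes by −180 × d + 180 × d = 0. At F = 150 it is 44,775 − 27,000 = 17,775 before and after.

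| F | SAP sum | 0–180 sum | Excess (% of 0–180) | d = 5 | d = 10 | d = 20 |
|---|---|---|---|---|---|---|
| 120 | 41,400 | 39,375 | 2,025 (5.1%) | −2.4% | −4.7% | −9.4% |
| 150 | 47,250 | 44,775 | 2,475 (5.5%) | −2.1% | −4.1% | −8.3% |
| 180 | 53,100 | 50,175 | 2,925 (5.8%) | −1.8% | −3.7% | −7.3% |
| 210 | 58,950 | 55,575 | 3,375 (6.1%) | −1.7% | −3.3% | −6.6% |

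The last three columns are changes in the SAP sum. Placing the fasting sample at 0 barely alters them: at F = 150 and d = 10, −1,950/47,250 = −4.1% becomes −1,800/44,775 = −4.0%.

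**Step 5: only the fasting sample falls.** The SAP sum changes by −15 × d. For d = 10 that is −150, or −0.25% to −0.36% over the range of F. Net incremental AUC changes by (180 − 7.5) × d = +1,725.

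**Step 6: sampling window.** The SAP does not say whether nominal or actual sample times enter the sum. At F = 150, with the last sample drawn at 183 min and actual times used, AUC_total is 47,250 + 3 × (250 + 220)/2 = 47,955. A cut at 180 drops that sample, so AUC0–180 ends at 150 min: 47,250 − 30 × (250 + 220)/2 = 40,200.

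**The case against.** **Incremental may not mean baseline-subtracted.** The phrase qualifies time, and its only example is a time interval. A reader might infer that a named baseline-subtracted endpoint has been omitted. The wording does not establish that. What stands is narrower: on the interval reading, the only interval defined equals the full test, so a second quantity is missing either way.

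**The −15 start does little harm to the comparison.** This is right. Both tests follow the same schedule, so the extra area is in both and largely cancels in the change. The 0–180 label also suggests that a start at 0 was intended. The SAP still gives no rule for placing the −15 sample.

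**Fasting glucose is reported separately.** FPG is a secondary endpoint, is scheduled on Days 1 and 16, is summarized by visit, and all data are listed by subject. A large shift would be visible. But FPG change uses the last value before the first insonification, which by the Schedule of Events is Day 15, while the OGTT baseline is Day 1. The planned FPG change is therefore not the fasting shift inside the AUC change, and visit summaries do not split that change within subjects.

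**Total AUC is legitimate and incremental AUC has its own weakness.** Both are true. Step 5 shows that incremental AUC rises when only fasting glucose falls, which could be read as worse tolerance. This argues for reporting both.

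**This is a descriptive pilot.** No sample size, error rate or decision rule depends on this AUC. That limits the severity but does not supply the missing definition.

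**Conclusion.** The point holds as a gap in endpoint definition. It should be fixed, but it does not threaten the study. On nominal times SAP 6.9 yields one number under two names, with a label that does not match the literal time span. No AUC in the plan distinguishes a parallel shift from a changed response to the drink.

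The weights of 195, 180 and 15 min follow from the schedule alone. The percentages rest on the assumed curves: about 2% to 9% for parallel falls of 5 to 20 mg/dL, and about 5% to 6% for the level error from the −15 start.

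Two stronger readings are not supported. A reader might infer that a fall in fasting glucose alone would look like better tolerance. The sizeable effect needs every sample to fall, and a fall in the fasting sample alone moves total AUC by only 15 × d. A reader might also infer that the −15 start, or the duplicated AUC, causes the fasting-shift problem. It comes only from the missing subtraction and is nearly the same size once the start is moved to 0.

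**What to change.** In SAP 6.9:

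1. Assign the −15 min fasting value to time 0.
2. Compute total AUC0–180 from 0 to 180 min and delete AUC_total as a separate quantity.
3. Define incremental AUC0–180 as AUC0–180 minus (fasting value × 180), as net area, with values below fasting counted as negative.
4. State that the 180-min sample enters at its nominal time, so that the ±3 min window cannot drop it.
5. Report both AUCs for Day 1, Day 16 and the within-subject change, next to the OGTT fasting value.
6. Say that incremental AUC is read together with total AUC and not in place of it, because it rises if only fasting glucose falls.

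The cost is two formulas and a few sentences in the SAP. All samples are already in the schedule, and neither study conduct nor the protocol has to change.
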